Specific Aim 1: To use incentive motivation tasks to evaluate the coupling between motivation and movement vigor in recently treated PD subjects before and after LDR induction.

Hypothesis 1A: LDR induction will result in partial restoration of movement vigor in response to monetary incentives in PD subjects in the “practical off” state.

Hypothesis 1B: The magnitude of partially restored movement vigor in response to monetary incentives will correlate with reduced bradykinesia in PD subjects in the “practical off” state.

Hypothesis 1C: Identical effects will be found with an incentive motivation task based on movement amplitude and one based on grip strength.

Rationale: A substantial body of data indicates that striatal DAergic neurotransmission mediates vigor – the speed, amplitude, force, or frequency of actions.²¹⁻²⁵ These different aspects of vigor have in common modulation of effort, ultimately the degree of energy expenditure required to accomplish actions. Vigor modulation is closely linked to the motivational role of striatal DAergic neurotransmission. Salamone and others argue persuasively that striatal DAergic neurotransmission is critical for efficient effort allocation by proportioning actions to perceived rewards – the fundamental process of motivation.²¹⁻²³ Several studies implicate aberrant movement vigor modulation as the underlying mechanism of PD bradykinesia. An influential experiment by Mazzoni et al. indicates that PD subjects exhibit aberrant estimation of effort-reward tradeoffs of movements.²⁶ These results were replicated by several groups using a variety of paradigms to assess movement vigor in PD subjects.²⁷⁻²⁹ These paradigms generally isolate modulation of movement velocity, force (e.g., grip strength), or amplitude as outcome measures. These outcome variables all reflect effort and in most paradigms, the chosen outcome variable (e.g., amplitude of reaching) is co-linear with other potential outcome variables (e.g., force of reaching).

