symptoms, they will be asked to squeeze a hand dynamometer at the outset of the experiment to measure the strength of their maximum voluntary contraction (MVC). All grip strength targets will be scaled to this value. Subsequently, subjects will undergo a series of trials in which they will be presented with an incentive cue that indicates the level of reward for that trial. They will be informed that on each of these trials they will earn a percentage of the incentive shown that is directly proportional to how hard they squeeze on that trial. While healthy individuals generally increase grip strength with increasing incentive values on this task, previous work has shown that PD patients are impaired in their ability to modulate their grip strength in this way. To ensure that any deficits found are due to motivational vigor and not simply a reflection of impaired muscle power, we will incorporate control trials in which PD subjects are instructed to increase grip strength to similar target levels of force without monetary incentives.

We will use a variant of the mouse task used in Panigrahi et al.³⁴ This task was inspired by tasks used in human PD studies.^{26,27} A spring loaded joystick that returns to a center position if no force is applied is used. Application of force to the joystick displaces it from the center and is monitored to detect the real-time trajectory of the movement. A water reward is delivered 1 second after the joystick passes a specified amplitude threshold. For human equivalent tasks, a flexible range of manipulanda (varying the force requirements) and flexible visuomotor feedback during training and/or testing are deployed. Varying force requirements for reward measure reward-effort coupling. Use of 2 incentive motivation tasks is complementary and provides a more stringent test of our hypothesis. As these tasks are different measures of movement vigor modulation, we should obtain similar and strongly correlated results. Confirmation of our hypothesis with the amplitude modulation task will provide reassurance that we are studying the same vigor modulation phenomenon studied in basic investigations. The grip strength modulation task is better suited to functional imaging experiments and will be a valuable platform for future experiments.

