e) Analysis Plan: Hypothesis 1A: Our primary comparisons will be performance on the incentive motivation tasks before and after LDR induction. We predict that improved performance on the incentive motivation tasks will be apparent between the OFF-No LDR and Practical OFF-LDR conditions but not in comparisons between the other conditions. Data will be analyzed via 2-Way Repeated Measures ANOVA followed by post-hoc tests with incentive level and treatment condition as the factors and multiple comparison adjustments. Based on the Schmidt et al. data³⁶, we estimate that achieving power of 0.9 at an effect size of $r^2 = 0.15$ requires complete data from 16 subjects. Based on experience with complex, serial imaging studies, we project a 10% dropout rate (~2 subjects). To compensate for dropouts, we will recruit 20 subjects. Hypothesis 1B: We will correlate changes in performance on the incentive motivation task with the change in tapping rates with Pearson or Spearman correlation tests. Hypothesis 1C: We will correlate the results of the amplitude modulation based and grip strength based incentive motivation tasks with Pearson or Spearman correlation tests.

Interpretations and Potential Problems: If our predictions are correct, we will validate the connection between the LDR and partial restoration of vigor modulation. Falsifying this hypothesis will be equally valuable as it would direct research on the LDR towards different features of striatal DA action. We may, for example, find a relationship between the SDR and improved vigor modulation, which would direct research towards the mechanisms of the SDR. As discussed above, prior experiments evaluating vigor modulation in PD have not taken the LDR into account. We may find no clear relationship between vigor modulation and bradykinesia. This would be important as it would cast doubt on the widely accepted concept that PD bradykinesia is the consequence of altered vigor modulation, and potentially re-direct research in this field.

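### Hypothesis 1C predicts identical effects in the two vigor tasks, but its only planned test, a correlation of undefined results, cannot compare the mean effects

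*Combined protocol and SAP*

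**What the plan says.** Hypothesis 1C, stated in section B and again in section C under Specific Aim 1, reads: "Identical effects will be found with an incentive motivation task based on movement amplitude and one based on grip strength". Procedures d) of Specific Aim 1 adds the expectation that "we should obtain similar and strongly correlated results". That expectation has two parts, similarity and correlation.

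The Analysis Plan (Specific Aim 1, part e) gives one analysis for it, by Pearson or Spearman coefficient: "We will correlate the results of the amplitude modulation based and grip strength based incentive motivation tasks". The sentence before, on Hypothesis 1B, is more specific: "We will correlate changes in performance on the incentive motivation task with the change in tapping rates". For 1C neither a change score nor any of the four measurement states is named.

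For Hypothesis 1A, "Our primary comparisons will be performance on the incentive motivation tasks before and after LDR induction". These are analysed by a two-way repeated-measures ANOVA "with incentive level and treatment condition as the factors and multiple comparison adjustments". Task is not a factor. No between-task comparison, common scale, margin or target correlation is given anywhere.

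**The concern.** The hypothesis is about the size of an effect in two tasks. The test is about whether subjects who score high on one task also score high on the other. These are different quantities, and each can hold without the other.

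If the results are levels, stable differences between patients, such as disease severity, can produce a strong correlation even when the LDR acts on one task only. If they are changes, the correlation reflects how far individual responses vary together. A similar response in every patient then gives a correlation near zero although the effects are identical. So 1C could be declared confirmed or refuted without its claim about equal effects having been examined.

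**Working it through.** **1. The plan's own figure.** The Analysis Plan states that "achieving power of 0.9 at an effect size of $r^2 = 0.15$ requires complete data from 16 subjects". Aim 2 gives the same 0.15 as η², so f² = 0.15/0.85 = 0.1765. For a within-subject ANOVA with m conditions and correlation ρ between them, λ = n·m·f²/(1−ρ), with (m−1) and (n−1)(m−1) degrees of freedom. Two-sided α = 0.05 and ρ are my assumptions.
- m = 2, ρ = 0.5: λ = 16×2×0.1765/0.5 = 11.3. Power is 0.88, and 17 subjects reach 0.90.
- m = 4, ρ = 0.3: λ = 16×4×0.1765/0.7 = 16.1. Power is 0.91.

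So 16 is reproducible for the 1A comparison. It was not derived for 1C.

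**2. The algebra.** For any constant c and any k > 0, r(A + c, B) = r(A, B) and r(kA, B) = r(A, B). Adding a constant LDR effect to one task, to both, or with opposite signs leaves r as it was. This step needs no assumption about variances.

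**3. Threshold.** With n = 16, t(0.975, 14) = 2.145, so the critical |r| = 2.145/√(14 + 2.145²) = 0.497.

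**4. Assumptions for size.** None of these is in the documents. The between-subject trait SD is 1, measurement error SD is 0.35, and the LDR effect is 0.48 trait SD. Percentages are simulated and good to about one point.

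**5. Levels, LDR effect in one task only.** Expected r ≈ ρ_T/(1 + 0.35²) = ρ_T/1.1225, where ρ_T is the trait correlation between tasks.

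| ρ_T | Expected r | Significant |
|---|---|---|
| 0.9 | 0.80 | about 98% |
| 0.5 | 0.45 | about 42% |
| 0.3 | 0.27 | about 17% |

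By step 2, the same percentages arise when the same constant effect is present in both tasks.

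**6. Changes, identical mean effects.** The error SD of a change is 0.35√2 = 0.495, with variance 0.245. Let individual responses have SD s and correlate 0.8 across tasks. Expected r ≈ 0.8s²/(s² + 0.245).

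| s (trait SD) | Expected r | Positive and significant |
|---|---|---|
| 0 | 0.00 | about 2% (chance) |
| 0.2 | 0.11 | about 6% |
| 0.5 | 0.40 | about 36% |
| 0.8 | 0.58 | about 69% |

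**7. A direct contrast, for comparison.** With a homogeneous response, the SD of the between-task difference in change is 0.495√2 = 0.70. With an effect of 0.48 in one task only, the noncentrality is 0.48×√16/0.70 = 2.74. A paired test of the task difference then detects it in about 73% of trials, and rejects in 5% when the effects are equal.

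**8. Precision.** t(0.95, 15) = 1.753. The 90% CI half-width is 1.753×0.70/4 = 0.31 SD, or 1.753×1/4 = 0.44 SD if the paired-difference SD is 1.

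**9. What 1A would show.** With the effect in one task only, a paired test in that task has noncentrality 0.48×4/0.495 = 3.88 and power of about 95%. The other task is non-significant in 95%. The pattern of one significant task and one not appears in about 0.95×0.95 = 0.90 of trials.

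**The case against.** The strongest reply has four parts.

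- **The correlation does part of the job.** It addresses the expectation in Procedures d) that the tasks be strongly correlated. This stands. Only the similarity half goes untested.
- **Hypothesis 1A covers both tasks.** An effect in one task only would usually be seen there (step 9). This stands as a practical safeguard. But finding one result significant and the other not is not a comparison of the two effects, and the plan does not connect 1C to it.
- **The alarming percentages are chosen points.** A reader might infer that the correlation would nearly always come out significant when only one task responds. The documents do not support that: they give no variances, the 98% needs levels and a trait correlation of 0.9, and the Hypothesis 1B sentence makes change scores a natural reading. On changes, a strong correlation with an effect in one task only needs some other shared variation, such as practice or day-to-day state. Likewise, the near-zero correlation under identical effects needs a nearly uniform response, whereas Hypothesis 1B presupposes that responses vary. The ranges matter more than any single figure.
- **Little else hangs on 1C.** A reader might infer that the link from the human tasks to the basic work rests on it. Procedures d) instead rests that reassurance on confirming the hypothesis with the amplitude task.

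One caution about the remedy also stands. A task-by-LDR contrast depends on how each task is scaled, and with 16 subjects a non-significant term would not show equality.

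**Conclusion.** The point holds as a mismatch between a hypothesis and its test. That a correlation carries no information on whether the mean LDR effects are equal is algebra, and no other analysis in the plan compares the effects between tasks. How often this would mislead cannot be fixed from the documents. It depends on whether levels or changes are correlated, on the trait correlation between tasks and on the spread of individual responses, and the ranges in steps 5 and 6 are wide. Confidence is high for the logic and low for any one percentage. The issue is confined to 1C and should be corrected. It does not undermine the primary 1A comparison or the figure of 16 completers.

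**What to change.** 1. Define the 1C correlation on changes from OFF-No LDR to Practical OFF-LDR, and label it a test of association between the tasks.
2. Add the between-task difference in standardised LDR effect (a task-by-LDR term) with its confidence interval. One option is to divide each task's incentive effect by its own OFF-No LDR between-subject SD. Report it as an estimate, state that it depends on the scaling, and do not read a non-significant term as proof of equality.
3. Reword 1C from identical effects to effects in the same direction and of comparable size. With 16 subjects the 90% interval extends about 0.31 to 0.44 SD either side (paired-difference SD 0.7 to 1, assumed), so equality cannot be shown tightly.

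The cost is one model term and some wording, using data already planned. No subjects or visits are added. The downside is a more modest claim.

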b) Subjects will be studied at pre-treatment baseline and 2-3 months after L-dopa treatment initiation and regimen stabilization. We will only enroll drug-naïve subjects about to start treatment with L-dopa. Subjects will be studied in OFF and ON acute treatment states at baseline and after LDR induction. There will be 4 measurement states: at baseline prior to chronic treatment initiation (OFF-No LDR); at baseline after a standard, acute oral dose (25/250 carbidopa/L-dopa) of L-dopa (ON-No LDR), 2 months after initiation of chronic, stable L-dopa treatment but with no L-dopa for 10-12 hours prior to evaluation (Practical OFF-LDR), and after subjects’ usual L-dopa dose (ON-LDR) (**Table 1**).

Table 1:

OFF-No LDR	Baseline - Treatment Naïve Subject
ON-No LDR	Baseline - Treatment Naïve Subject After Acute L-Dopa
OFF-LDR	Chronically Treated – “Practical Off” State
ON-LDR	Chronically Treated – After Usual L-Dopa

Practical ON and OFF state measurements will be counterbalanced across individuals. We will recruit both male and female PD subjects, though we expect more male subjects as PD is more common in men. This is a within subjects design and randomization per se is not used. Blinding of study conditions is not feasible. It would be potentially interesting to include a placebo LDR induction arm, but denying PD subjects effective treatment is not ethical. Data analysis will be blinded. It would also be interesting to include a normal subject arm, but this is ethically problematic as it would involve chronic L-dopa treatment. If, however, we obtain results confirming our hypotheses, we will explore inclusion of normal controls in the next phase of experiments.

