Rationale: The long half-life of the LDR indicates that it is based on long-term DA mediated striatal plasticity. The computational model of Niv et al. suggests that accurate vigor modulation requires a striatal DA signaling “recording” the long-term prior average value of rewards. Rodent and non-human primate lesion experiments suggest that the striatum mediates estimates of prior reward histories.^{37,38} Studying saccadic eye movements in non-human primates, Hikosaka and colleagues described a basal ganglia mechanism stably encoding values of visual stimuli to modulate the vigor of saccadic eye movements.^{39,40} Hikosaka et al. presented animals with a large set of fractal images, training them to associate a subset with rewards. Weeks to months later and in unrewarded conditions, animals are exposed to groups of fractal images containing some images associated previously with rewards. Saccadic eye movement vigor was measured. Images associated previously with rewards evoked greater saccadic vigor. In detailed physiologic experiments, Hikosaka et al. established that activity of DAergic nigrostriatal neurons projecting to the caudate nucleus tail are critical for this phenomenon. This demonstration of long-term stable action-value association has features required of a DAergic mechanism “recording” reward history and underpinning vigor modulation.

If this phenomenon underpins vigor modulation, then DRT partial restoration of DAergic signaling in this circuit is a plausible substrate for the LDR. LDR induction is predicted to improve saccadic eye movement vigor in tasks analogous to that used by Hikosaka et al.

Procedures: Subject recruitment, characterization, and test conditions are as described in **Specific Aim 1**.

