It is not feasible to train PD subjects on hundreds of fractal images. We will use an analogous task validated well in humans; value driven attentional oculomotor capture (VDAOC).⁴¹⁻⁴³ A probabilistic learning task is used to train subjects to associate a salient visual stimulus (color) with reward. In a test phase, the previously rewarded stimulus is presented in task-irrelevant context as a distractor. Saccades to the test phase target and distractor are assessed, including percentage of saccades to distractor or target, saccade latency, and saccade duration. Previously rewarded distractor stimuli capture initial saccades and the magnitude of VDAOC is assessed. This task is accompanied by striatal dopamine release.⁴⁴ Subjects are trained in a single session and attentional capture is remarkably durable; it persists in test phase experiments months after a single training session.⁴⁵ To duplicate the approach used by Hikosaka et al., PD subjects will be trained on reward-color association prior to initiation of L-dopa therapy. VDAOC will be measured in 4 measurement states described above (**Table 1**). Saccades will be evaluated with an Eyelink tracker with a sampling rate of 250 Hz. If we again assume a modest effect size of $\eta^2 = 0.15$, 16 subjects will be sufficient to achieve a power of 0.9. To guard against dropouts, we will target enrolling 20 subjects. Data analysis approach will be similar to that proposed for **Specific Aim 1**.

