Interpretations and Potential Problems: Straightforward interpretation of this experiment presupposes validation of our hypothesis that LDR induction is associated with improved modulation of vigor as tested in **Specific Aim 1** experiments. Assuming validation of our primary hypothesis, we predict that LDR induction will be associated with improved saccadic eye movement vigor (VDOAC magnitude). The analysis approach will be similar to that used for **Specific Aim 1** experiments. The primary comparison will be between saccadic vigor in OFF-No LDR and Practical OFF-LDR conditions. If LDR induction is associated with improved saccadic vigor in the context of successful **Specific Aim 1** experiments, we will have evidence supporting the hypothesis that the stable striatal DAergic signaling described by Hikosaka’s group underpins the LDR. This would be an excellent point of departure for future experiments on LDR mechanisms. This experiment will have value even if we falsify **Hypothesis 1**. Regardless of the outcome of the **SA1**

experiments, success with this experiment would support the existence in humans of the interesting and potentially important phenomenon described by Hikosaka et al. in monkeys. It's possible that we might validate **Hypothesis 1** but falsify **Hypothesis 2**. That result would certainly point away from the mechanism described by Hikosaka et al. as underlying the LDR. An alternative interpretation then would be that the dopamine deficient (PD) state impairs value encoding. This could be evaluated in subsequent experiments in which different colors are associated with reward in different training sessions during each of our measurement conditions.

Potential obstacles and responses to problems associated with this experiment are those outlined above for **Specific Aim 1** experiments. This task has not been used in a patient population and a more prolonged training phase may be needed. Initial experiments will assess this potential issue.

D. Recruitment and Retention:

Subjects will include 30-40 with Parkinson disease (PD). For experiments for **SA1** and **SA2**, our power estimates indicate that 16 participants will be adequate for each experiment. We project recruiting 20 subjects for each experiment to compensate for possible dropouts. A number of subjects will participate in both **SA1** and **SA2** experiments.

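### Aim 2 cannot separate the LDR effect from time since training and repeated testing, so a null does not certainly point away from the mechanism

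*Combined protocol and SAP*

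**What the plan says.** **Training and testing** (section C, Specific Aim 2, Procedures). Training is given once, before treatment: "PD subjects will be trained on reward-color association prior to initiation of L-dopa therapy". The trained value is then tested repeatedly: "VDAOC will be measured in 4 measurement states described above". On the test itself: "In a test phase, the previously rewarded stimulus is presented in task-irrelevant context as a distractor". On retention: "Subjects are trained in a single session and attentional capture is remarkably durable; it persists in test phase experiments months after a single training session".

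**Order of states** (section C, Specific Aim 1, Procedures b). "Subjects will be studied at pre-treatment baseline and 2-3 months after L-dopa treatment initiation and regimen stabilization". The two No-LDR states therefore always precede the two LDR states. Only ON and OFF order is counterbalanced. The plan explains on ethical grounds why it has neither a placebo LDR arm nor a normal-subject arm.

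**Interpretation** (section C, Specific Aim 2, Interpretations and Potential Problems). The primary comparison is OFF-No LDR against Practical OFF-LDR, and an increase in capture is predicted. If Hypothesis 1 is validated but Hypothesis 2 is falsified, the plan says: "That result would certainly point away from the mechanism". It then offers one alternative, that the dopamine-deficient state impairs value encoding, to be examined in later experiments with a different colour for each state. It also concedes: "This task has not been used in a patient population and a more prolonged training phase may be needed", and says initial experiments will look at this.

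**The concern.** The contrast that decides Hypothesis 2 compares an early test of a learned association with a later test of the same association. Three things differ between the two: LDR status, time since training, and the number of earlier tests. No feature of the design or analysis separates them. If some learned value is lost, capture falls in the state where the hypothesis predicts a rise, and a real LDR effect could be hidden.

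A null would then have at least three explanations: no LDR effect, an association that faded, or an association that was never learned. The plan names the third but not the second, and still attaches the word *certainly* to the first. What is at stake is a candidate mechanism being set aside on evidence that cannot carry that conclusion.

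**Working it through.** **1. Order.** Number the tests 1 to 4. If ON and OFF are counterbalanced within each phase, OFF-No LDR is test 1 or 2 and Practical OFF-LDR is test 3 or 4. If counterbalancing applies only to the chronic phase, which the text also allows, OFF-No LDR is always test 1. On either reading Practical OFF-LDR is always later, with more prior tests.

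**2. The plan's sample size.** Inputs from Specific Aim 2, Procedures: η² = 0.15, 16 subjects, power 0.9. Alpha and the within-subject correlation ρ are not stated; I assume two-sided 0.05.
- f² = 0.15/0.85 = 0.1765, so f = 0.420.
- Repeated-measures noncentrality is λ = f²·n·m/(1−ρ), with m states.
- m = 2, ρ = 0.5, n = 16: λ = 0.1765×16×2/0.5 = 11.3, power 0.881; 17 subjects are needed for 0.90.
- m = 4, ρ = 0.3, n = 16: λ = 0.1765×16×4/0.7 = 16.1, power 0.913.
- With m = 2 the requirement runs from 32 subjects at ρ = 0 to 9 at ρ = 0.8.

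So 16 is reproducible under ordinary assumptions. It makes no allowance for downward drift between the baseline and LDR states.

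**3. Illustration: drift cancels part of the gain.** Let dz be the mean paired difference divided by its standard deviation. A value of 0.868 gives power 0.90 at n = 16 (F test on 1 and 15 df, λ = n·dz²). If loss of learned value cancels a fraction k of the gain, the effective value is 0.868(1−k).

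| k (assumed) | effective dz | power at n = 16 | n for power 0.90 |
|---|---|---|---|
| 0% | 0.868 | 0.90 | 16 |
| 10% | 0.781 | 0.83 | 20 |
| 25% | 0.651 | 0.68 | 27 |
| 50% | 0.434 | 0.37 | 58 |
| 75% | 0.217 | 0.13 | 226 |
| 100% | 0 | 0.05 | none |

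**4. Illustration: loss per test.** Suppose capture falls by a fraction q at each test and there is no LDR effect. With counterbalancing in both phases, the expected ratio of Practical OFF-LDR to OFF-No LDR is [(1−q)² + (1−q)³] / [1 + (1−q)] = (1−q)². For q = 5%, 10%, 20% this is 0.90, 0.81, 0.64. The true gain needed merely to show no change is 1/(1−q)² − 1 = 11%, 23%, 56%. If OFF-No LDR is always first, the ratio is [(1−q)² + (1−q)³]/2 = 0.88, 0.77, 0.58. The documents supply neither q nor k.

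**5. What a non-significant result excludes.** At n = 16 the 95% half-width, in standard deviations of the paired difference, is t(0.975, 15 df)/√16 = 2.131/4 = 0.533. An observed dz below 0.533 is non-significant. The interval excludes 0.868 only if the observed dz is below 0.868 − 0.533 = 0.335. Results between 0.335 and 0.533 are therefore null but do not rule out the planned effect, even without drift. The planned dz itself depends on ρ: dz = f·√(2/(1−ρ)) = 0.594, 0.840 and 1.328 at ρ = 0, 0.5 and 0.8.

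**6. Can the analysis adjust for test number?** Prior tests number 0 and 1 before LDR induction, 2 and 3 after. The correlation with phase (0, 0, 1, 1) is 0.5/(1.118×0.5) = 0.89. A session-count term would be nearly collinear with the effect of interest and close to uninformative at n = 16.

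**The case against.** The strongest reply is that the only evidence in the documents on retention favours the plan: capture is described as lasting months after one training session, which is about the interval used here. That stands against any statement that capture *will* fall. It does not close the question. Persisting is not the same as undiminished, the statement is not said to cover repeated testing without retraining, and the plan says the task is untried in patients. Practice could also move the contrast, in either direction.

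Second, a reader might infer that the test phase is unrewarded and spread over four sessions, so that extinction is built in. The documents do not say so. Lack of reward is stated only for the animal work in the Aim 2 Rationale ("Weeks to months later and in unrewarded conditions, animals are exposed to groups of fractal images"). For the human task it is an inference from the stimulus being previously rewarded and task-irrelevant, and from the aim of copying the animal approach. The text speaks of measurement states and does not say whether two share a visit.

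Third, a reader might infer that the plan treats any null as unqualified proof against the mechanism. It does not. The sentence is conditional on Hypothesis 1 being validated, impaired encoding follows at once as an alternative, and initial experiments on training length are promised. That covers the never-learned explanation in part; it leaves out fading and repeated testing.

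Fourth, a fixed order is unavoidable when subjects must start drug-naïve, the plan gives reasons for having no control arm, and Aim 2 is the secondary objective. All true. These are reasons to limit the conclusion, not to demand a redesign.

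**Conclusion.** The concern holds as a limit on interpretation. The primary contrast of Aim 2 is fully confounded with time since training and with prior testing, any loss of learned value would bias against Hypothesis 2, and the plan's reading of a null is stronger than the design can support.

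The size of the bias is unknown. The figures of 0.37 power with half the gain cancelled, and 0.90 to 0.64 for capture ratios with both phases counterbalanced, rest on assumed losses and show only what would follow. It would be tempting to conclude that decay or extinction does lower capture, or that the sample size is wrong. The documents support neither: they give no decrement, and 16 subjects is reproducible.

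The gap in the wording does not depend on those assumptions. Listing impaired encoding as an alternative is already inconsistent with *certainly*, and fading and repeated testing are missing from the list.

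**What to change.** In Specific Aim 2, Interpretations and Potential Problems, replace the sentence containing *certainly* with a conditional rule, for example:

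> If Hypothesis 1 is validated and Hypothesis 2 is not supported, the result counts against the mechanism only if (a) the association was shown to be learned, by performance at the end of training or by capture above zero in at least one pre-treatment state, OFF or ON; and (b) the confidence interval for the OFF-No LDR versus Practical OFF-LDR difference excludes the planned effect. Otherwise the result is inconclusive. Alternatives are impaired encoding, fading of the learned value, and effects of repeated testing. Because the order of LDR states is fixed, fading cannot be fully excluded even when (a) and (b) hold.

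Condition (a) should accept either pre-treatment state. Low capture in OFF-No LDR alone may be the very deficit under study, so requiring capture there could not tell failed learning from that deficit. For (b), state the planned effect on the scale of the paired difference before analysis, with the assumed ρ, because the criterion depends on it.

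Do not add a session-count sensitivity term. A second trained colour held back for the LDR states would remove earlier testing of that colour, but it divides the training where the plan already fears too little, and it leaves elapsed time and practice untouched. It is an option to consider in the planned initial experiments, not a required change.

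The cost is a few sentences and no added visits. The real downside is that a null supports a weaker conclusion.
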